We propose to recruit a prospective cohort of persons with TBI to compare effects of Bright White Light exposure to Red Light (RL) exposure. Light therapy treatments will be given daily in the morning for up to 10 days, and an Actiwatch will be worn that records movements for the entirety of the study. We will utilize objective assessments of sleep quality, subjective mood report, rate sleepiness and fatigue and complete measures of attention and participation in rehabilitation therapies to explore the

effects of light exposure in the acute inpatient rehabilitation setting. We will also evaluate the anticipated device costs and staff burden involved in utilizing light therapy exposure in the inpatient rehabilitation clinical setting. An overview of study procedures with timeline is described in Figure 1 below with further details in the sections that follow.

Figure 1. Overview of Study Procedures for TWILIGHT

VI. Screening for Eligibility:

Although subjects will be screened for this study concurrent with screening for eligibility for enrollment into the Traumatic Brain Injury Model System (TBIMS) study (Traumatic Brain Injury Model Systems, 2013), these are independent studies and subjects will have the choice to enroll in both, neither, or either one. The TBI Model Systems program, sponsored by the National Institute on Disability and Rehabilitation Research (NIDRR), is the largest longitudinal study of TBI in the nation. NIDRR awards 5 year grant awards to institutions that are national leaders in medical research and patient care and these. Institutions which receive this distinction are collectively termed, the TBI Model Systems. As part of the TBI Model Systems, the University of Washington TBI Model Systems research team is recognized as providing the highest level of comprehensive specialty services from the point of injury through chronic care stages, including re-entry into full community life. The current grant cycle is for the 2012-2017 time period, and one of the areas of interest for the UW TBI Model Systems research team is the treatment of sleep difficulties after TBI.

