Days 3-13: Each morning for 10 days, the research and/or nursing staff will set up the Litebook® device in the marked out area of the bedside table. The light will be between 12 and 24 inches from the subject, allowing light to reach the subject's eyes. The subject will be in front of the device for 30 minutes, eating or otherwise doing relaxing activities and will have the eyes open. Both BWL and RL will be delivered using a Litebook® (The Litebook Company Ltd; Medicine Hat, Alberta, Canada). The Litebook® is a small (6 inch x 5 inch x 1 inch) unit with an attached stand that is placed 12-24 inches from the user's face and within 45 degrees of the visual field per manufacture guidance. Both the BWL and RL devices contain a data log to track the times at which the light box is turned off and on allowing the total time of exposure to be calculated. The cases for the BWL and RL units are visually identical. Research Staff will setup the Litebook ® on the bedside/over bed table as part of the subjects' morning/breakfast daily routine. The research staff will check in with nursing staff and the patient/LAR regarding adverse effects each day. Study medical staff will also be available for study questions or problems at other times and the patient's primary medical service will also be following for their overall medical care per routine. Nursing staff will be trained regarding the light exposure protocol as part of preparation for the study and the individualized setup for each subject will be reviewed and diagrammed in their room on enrollment. Subjects will receive 10 morning sessions of their assigned light therapy (BWL vs. RL).

Additional Data Collected

- 1) Sleep Logs: Sleep logs will be integrated with overnight nursing rounds. Trained nursing staff will perform regular ratings every hour of sleep/wakefulness between 2200-0600 using the Makley Scale, a 4-point ordinal scale ranging from 0 (asleep) to 3 (awake). This paper sleep log will be collected daily by the research study staff. This is part of routine rehabilitation care and will not add any sleep disruption for study participants. Sleep logs will be used as one tool to help interpret overall actigraphy data patterns during analysis.
- 2) Therapy Participation: The physical therapist will be asked by the research staff to rate at both baseline days and on the final two days outcome assessment time points.

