- 3) Clinical Staff feedback: phototherapy intervention will rated using a likert scale on the following categories:

- a. Ease of use
- b. Perceived relevance to rehabilitation care
- c. Impression of effectiveness.

Post Light Therapy Outcome Assessment

Day 13: At the conclusion of the light therapy sessions (and prior to discharge from rehabilitation), a blinded Outcomes Examiner will complete the post therapy outcome assessment. This assessment will include the following:

- Symbol Digit Modalities Test
- Positive and Negative Affect Schedule (PANAS)
- Barrow Neurological Fatigue Scale

XII. Data Analysis

The primary outcome is the between-group difference (BWL vs. RL exposure) in average sleep efficiency at baseline compared to after 10 days of light treatment. ANOVA will be used to compare groups controlling for demographics, injury severity, and use of medications.

Secondary outcomes (mood, therapy participation, attention, daytime sleepiness/fatigue) between groups assessed at baseline and after 10 days of light therapy will be compared using repeated measures ANOVA. FIMTM efficiency and inpatient rehabilitation length of stay will also be compared between groups using ANOVA controlling for the same variables as the primary outcome. Descriptive analysis will summarize responses to the nursing burden questions including estimated staff time for the intervention.

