Treatment conducted as part of this study may be of benefit to an individual participant (e.g. progress on cognitive testing over time). The main sharing of study results, however, will be with the general public and medical community which may benefit from our study outcome. We plan to report our findings in published material and at medical conferences. Data sharing will follow the TBIMS protocol.

XIV. Safety and Adverse Events

Each subject will be followed medically daily by their rehabilitation resident and attending physicians and have 24 hour monitoring by rehabilitation nursing. The research assistant at each site will check in with the patient/LAR and nursing staff daily Monday through Friday to elicit any concerns. [name]. a psychiatrist in the University of Washington's Department of Rehabilitation Medicine has expertise in TBI treatment and research procedures and has agreed to be the Data Safety Monitor (DSM). He will receive a quarterly summary of all Adverse Events for review and will be contacted by the study team within 24 hours of any Serious Adverse Event to review with the study physician. Any serious adverse event will be reported to the Human Subjects Division as well immediately. At quarterly intervals after subject enrollment begins, the DSM will review and evaluate the studies' clinical efficacy and safety data. The DSM will monitor study progress, examine adverse events (AEs) and serious adverse events (SAEs), and recommend the continuation without change, suspension, or termination of a study.

XV. Definitions

Unanticipated Problems Involving Risk to Subjects or Others

Any incident, experience, or outcome that meets all of the following criteria:

- Unexpected in nature, severity, or frequency (i.e. not described in study-related documents such as the IRB-approved protocol or consent form, the investigators brochure, etc)
- Related or possibly related to participation in the research (i.e. possibly related means there is a reasonable possibility that the incident experience, or outcome may have been caused by the procedures involved in the research)
- Suggests that the research places subjects or others at greater risk of harm (including physical, psychological, economic, or social harm).

Adverse Event

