- 5. How difficult is it for me to stay alert during activities? _____
- 6. How difficult is it for me to build my energy level once I wake up in the morning? _____
- 7. How difficult is it for me to stay out of my bed during the day? _____
- 8. How difficult is it for me to stay alert when I am not involved in something? _____
- 9. How difficult is it for me to attend to something without becoming sleepy? _____
- 10. How difficult is it for me to last the day without taking a nap? _____

11. Please circle your **OVERALL** level of fatigue since your injury:

0	1	2	3	4	5	6	7	8	9	10
No problem										Severe Problem

Quarterly Staff Survey

If you have been involved in the care of a patient enrolled in the TWILIGHT Study in the past three months please answer the questions below.

Date: _____

Please check one:

- Rehabilitation Nurse
- Rehabilitation Therapist (PT, OT, SLP, TR)
- Other

Please indicate whether you agree or disagree with the following statements:

Q1: It was easy to integrate light therapy into patient care.

1	2	3	4	5
Strongly Disagree	Disagree	Neither agree or disagree	Agree	Strongly Agree

Q2: Light therapy did not increase my work load.

1	2	3	4	5
Strongly Disagree	Disagree	Neither agree or disagree	Agree	Strongly Agree

Q3: Light therapy should be offered as a routine treatment option in in-patient rehabilitation.

1	2	3	4	5
Strongly Disagree	Disagree	Neither agree or disagree	Agree	Strongly Agree

Comments?

Overview for Study Participants

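### The plan is inconsistent on who sets up the light and records neither who delivered a session nor the minutes taken, so the staff-burden results may understate the load on unit staff

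*Combined protocol and SAP*

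**What the plan says.** Section V of the combined protocol and SAP commits the study to evaluating device costs and the "staff burden involved in utilizing light therapy exposure in the inpatient rehabilitation clinical setting". Hypothesis 3a in Section IV rests on Likert ratings by staff of whether bright white light is a reasonable addition to care.

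Section XI, under Light Therapy, describes delivery twice. The opening sentence reads "Each morning for 10 days, the research and/or nursing staff will set up the Litebook® device". Later in the same paragraph: "Research Staff will setup the Litebook ® on the bedside/over bed table". The paragraph also says "Nursing staff will be trained regarding the light exposure protocol as part of preparation for the study", and that each subject's set-up is diagrammed in the room.

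On analysis, Section XII says "Descriptive analysis will summarize responses to the nursing burden questions including estimated staff time for the intervention".

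The instrument is the Quarterly Staff Survey in the Appendix. It is addressed to staff as follows: "If you have been involved in the care of a patient enrolled in the TWILIGHT Study in the past three months". Respondents tick nurse, therapist or other, and rate three statements on a five-point agreement scale: item 1 on ease of integration, item 2 ("Light therapy did not increase my work load"), and item 3 on whether light therapy should be a routine option. A free-text comment line follows.

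**The concern.** Staff burden in routine care is the time and effort that unit staff would have to supply if no research team were present. To estimate it, one needs to know who did the work in the trial and how long it took. If research staff set up many of the sessions, a nurse or therapist can truthfully agree that light therapy added nothing to their own workload, and that answer says little about the cost of delivering it. If the minutes that research staff spend are not counted, the time estimate falls short as well.

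At stake is the feasibility conclusion. Section III presents integration into usual care as something the study investigates, and Aim 3 is meant to inform the design of future studies. A favourable burden figure obtained partly under research-staff delivery could be read as the burden of delivery by the unit.

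**Working it through.** The plan states no number on this point: no survey sample size, no threshold for Hypothesis 3a, no expected share of sessions set up by nurses and no expected time per session. There is therefore no figure to reproduce. The check compares what the objective needs with what is collected, and then shows how the missing quantities would enter the result.

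**What is needed against what is described**

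- *Who set up each session.* Section XI gives two answers. Table 1 lists light exposure time, and the device log holds on and off times. Neither identifies a person.
- *Minutes of staff time.* Section XII promises an estimate. The device log measures exposure, not set-up effort. The printed survey has no time question, and the description of the Clinician Feasibility Survey in Section X.D lists ease of use, relevance and impression of effectiveness, not time.
- *Whether the respondent delivered light.* The survey asks about involvement in the patient's care. The role box identifies therapists, to whom the documents give no set-up role. It cannot separate nurses who set up sessions from nurses who did not.

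**Workload rating (survey item 2)**

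Let f be the share of respondents who set up the light, a the proportion of them who agree that workload did not rise, and b the proportion agreeing among the rest. Over all respondents,

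observed agreement = f·a + (1 − f)·b,

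and the excess over the deliverers' own figure is (1 − f)·(b − a). All three inputs are assumptions, because the documents give none of them.

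| f | a = 50%, b = 90% | a = 70%, b = 80% |
|---|---|---|
| 100% | 50% | 70% |
| 75% | 60% | 72.5% |
| 50% | 70% | 75% |
| 25% | 80% | 77.5% |
| 0% | 90% | 80% |

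For example, at f = 50% in the first column: 0.5 × 50 + 0.5 × 90 = 70%. The shift is upward whenever b exceeds a. It is up to 40 points in one column and at most 10 in the other. If non-deliverers mostly chose the neutral category, b could fall below a and the shift would reverse.

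**Staff time**

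Let p be the share of sessions set up by unit staff, and assume equal minutes per session. An estimate that counted only unit-staff minutes would capture a fraction p of the set-up time and miss 1 − p. The documents leave p anywhere between 0 and 1. Section XII does not say whose minutes count.

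**The case against.** There is a good deal to be said on the other side.

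- *Nurses may deliver many sessions.* The first set-up sentence includes them, they are trained, and the set-up is diagrammed in the room. A reader who took only the later sentence might infer that research staff set up every session and that the result is therefore biased. The documents do not support that. They show an inconsistency and a risk.
- *A weekday calculation is tempting but unsupported.* Ten consecutive mornings contain 2, 2, 2, 3, 4, 4 or 3 weekend days for starts from Monday to Sunday, a mean of 20/7 = 2.86. A reader might infer that nurses set up only about 29% of sessions and that about 71% of set-up time goes uncounted. This relies on the statement in Section XIV that research assistants check in "daily Monday through Friday to elicit any concerns". That sentence concerns check-ins about concerns, not device set-up or presence on the unit, and Section XI has research staff checking in every day.
- *Role is already recorded.* Therapists can be separated without changing the form, and no passage commits to pooling all respondents. This stands. The gap that remains is among nurses.
- *Research-staff time is not expressly excluded.* Section XII speaks of staff time for the intervention. This stands too, but no source for the minutes is described.
- *A form may exist elsewhere.* The Manual of Procedures and the data sheet mentioned in Table 1 are not reproduced, so the point is limited to records that the documents describe.
- *Burden is wider than set-up, and Hypothesis 3a is wider than workload.* A 30-minute morning session can affect anyone caring for the patient, so non-deliverers can answer items 1 and 2 validly. Item 3 is closest to the hypothesis and needs no delivery experience.

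These arguments limit the claim. They do not supply the missing information on who delivered the sessions or how long set-up took.

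**Conclusion.** The concern holds as a gap in measurement. Section XI should say one thing about who sets up the light, and the plan as described cannot link workload ratings to delivery or supply the staff time it promises. Once the surveys are in, the printed form gives no way to divide nurses into those who delivered and those who did not, so the gap has to be closed during data collection.

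The likely direction is understatement of the burden on unit staff. That rests on two conditions: research staff carry out some of the set-up, and those who did not deliver agree with item 2 more often than those who did. The size cannot be derived from the documents, and the percentages in the table show only how the result depends on assumed inputs.

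The consequence is confined to the descriptive Aim 3 results on burden. The sleep-efficiency comparison and the other efficacy outcomes are untouched. This is an inexpensive improvement worth making, not a flaw in the trial's main inference.

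**What to change.** 1. Reconcile the two set-up sentences in Section XI.
2. For each session, record whether unit nursing or research staff set up the light, and the minutes spent.
3. Add one item to the Quarterly Staff Survey, covering the same three months: I set up or took down the light myself, yes or no.
4. In Section XII, state that items 1 and 2 will be reported by role and by delivered yes/no, that research-staff minutes are included in the staff-time estimate, and that the percentage of sessions set up by unit staff will be shown beside the result for Hypothesis 3a.

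Ratings from staff who did not deliver stay in the report; they are shown separately.

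The cost is a short entry per session, which may need a new form because the only log described is the device's own on/off record. It also includes one more survey item, small subgroups in a descriptive table, and possibly a less favourable burden figure. Randomisation, sample size and the intervention do not change.

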Aim 1: In persons with TBI, prospectively compare overnight sleep efficiency in a cohort exposed to morning Bright White Light with a comparison group exposed to Red Light in an acute inpatient rehabilitation setting.

Aim 2: Explore the relationship between Bright White Light exposure during inpatient rehabilitation after TBI and mood, therapy participation, attention, rate of functional recovery and length of stay.

Aim 3: Develop and describe sleep study procedures on the inpatient rehabilitation unit for persons with TBI to support optimal and feasible design of future studies in this important area.

Research Hypothesis:

In persons with TBI, prospectively compare overnight sleep in a cohort exposed to morning Bright White Light with a comparison group exposed to Red Light in an acute inpatient rehabilitation setting.

Hypothesis 1: Individuals exposed to Bright White Light for 30 minutes each morning will have better sleep compared to the Red Light exposure group, as measured by sleep efficiency.

Hypothesis 2: Individuals with daily morning Bright White Light exposure will have better mood (as measured by the Positive and Negative Affective Schedule, PANAS), therapy participation (as measured by a 0-100 therapist rating) and attention (as measured by the Symbol Digit Modalities Test) at 10 days compared to individuals with daily Red Light exposure. The group exposed to Bright White Light will also have less daytime sleepiness and fatigue (as measured by the Karolinska Sleepiness Scale (KSS) and the Barrow Neurological Institute Fatigue Scale (BNI-FS), a faster rate of functional recovery as measured by FIM™ efficiency for the rehabilitation stay and a shorter length of stay compared to those in the Red Light group

Hypothesis 3a: Bright White Light exposure will be rated as a reasonable addition to clinical care by staff using Likert scale ratings. Categorize and quantify rates of any side effects of Bright White Light and Red Light exposure in persons with TBI during inpatient rehabilitation.

Hypothesis 3b: Bright White Light and Red Light exposure will be generally well tolerated with side effect profiles and rates similar to those observed in previous studies with other populations.

[figure not shown]
See Appendix for Flowchart on Specific Aims of this study

V. Study Description

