Medical History	Diagnoses, medications at enrollment, symptoms, associated injuries (ICD-9 codes), vital signs	X		
Berlin questionnaire	Sleep apnea	X		
Clinician Rating: Delirium Rating Scale Revised 98 Item 1	Sleep disturbance	X		
Makley scale	Sleep disturbance	X	X	
Actigraphy	Sleep parameters	X	X	
Light Therapy Time	Light exposure time		X	
Medication categories	Potential confounders (see data sheet)	X		X
FIM™ Scores and Efficiency	Functional score	X		X
Hospitalization	Acute LOS, Rehab LOS	X		X
Symbol Digit Modalities Test	Attention	X		X
PANAS	Mood	X		X
Therapy participation	Function	X		X
Karolinska Sleepiness Scale	Daytime sleepiness	X		X
Barrow Neurological Institute Fatigue Scale	Daytime fatigue	X		X

A. Screening Measures:

The following data will be used as descriptive characteristics of the subjects upon study completion. Initially this data will be used during the screening process to ensure appropriate patients are approached for participation:

- **Demographics:** Age, gender, race/ethnicity, weight (kg), height (cm), BMI (calculated).

- **Injury Characteristics:** Time since injury, Post-resuscitation GCS score, duration of PTA as measured by TBIMS procedures using the Galveston Orientation and Amnesia Test (GOAT), associated injuries including ICD codes.
- **Medical History:** Current diagnoses, past diagnoses, medications (at enrollment, during treatment and at outcome measure), vital signs.
- **Berlin Questionnaire** (Netzer NC, 1999): The 10-item questionnaire consists of 3 categories related to the risk of having sleep apnea. Patients can be classified into High Risk or Low Risk based on their responses to the individual items and their overall scores in the symptom categories.

B. Randomization Measure:

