- Therapy Participation: Participation in rehabilitation therapies will be evaluated at enrollment and again after light therapy (day 13) by the subject's therapist using a 0-100 scale of cooperation with therapy that has been previously utilized in this population.[45]
- Karolinska Sleepiness Scale (KSS): The KSS is a well-validated, widely used single question survey that examines current sleepiness.
- Barrow Neurological Institute Fatigue Scale (BNI-FS): The BNI-FS is a scale that was designed to examine fatigue during acute recovery from TBI. It has good internal consistency and appears to specifically examine a single psychometric construct of fatigue in patients with TBI (Wäljas M, 2012).
- Clinician Feasibility Survey: This is a likert scale survey to assess phototherapy intervention for ease of use, perceived relevance to rehabilitation care, and impression of effectiveness. This survey will be available in paper and electronic versions.

XI. Study Procedures:

Screening and Enrollment:

Patients' medical records will be screened for inclusion/exclusion criteria. Informed consent will be obtained from the subjects after they have been determined to be cognitively capable to consent for the study. A subject will be considered unable to give independent consent if they are still in PTA (as measured by the Galveston Orientation & Amnesia Test (GOAT), with a score <76) or their medical record at the time of enrollment specifies that they are unable for other reasons to independently consent. If a subject is unable to consider consent independently, proxy consent will be obtained from the legally authorized representative (LAR). This process is part of obtaining informed consent for the TBI Model System study. In addition, clinical staff and research staff have established communication lines to approach patients at appropriate times that do not interfere with patient clinical care.

Baseline and Randomization:

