Day 0-1 (2 days): After determining eligibility, the participant will be fitted with an Actiwatch (actigraphy) for continuous monitoring of activity levels both during the day and night (American Sleep Disorders Association, 1995). The Actiwatch will be worn continuously (with removal as needed for hygiene, shower or other clinical care) from enrollment to outcome measurement. Actiwatches will be fully charged and cleared of all previous data before being provided to a subject. Units will be set to record activity data in 60-second epochs. Actiwatches have sufficient built-in memory capacity and battery life to be used for approximately 30 days without recharging. Additionally, sleep logs that rate patient sleep are filled out every hour, between the hours of 2200-0600, this information is then obtained

as completion of the Makley scale. A complete review of symptoms and medical history will be obtained from the subject, LAR, and medical records.

Day 2: Baseline data collection is obtained (See Appendix for Baseline Data Collection Forms). Measures collected include: Symbol Digit Modalities Test, Positive and Negative Affect Schedule (PANAS), Barrow Neurological Fatigue Scale. Clinical Staff, will be asked if there was sleep difficulties and therapist will be asked to rate therapy participation for that day.

Day 2: Randomization. After baseline testing is completed, subjects will be randomized (50:50) using a 2-level stratification design based on two pieces of information:

- 1) Center (U. Washington-Seattle, Baylor-Dallas, Mount Sinai-New York) and
- 2) Severity of Sleep Disturbance using Delirium Rating Scale-Revised 98 Item 1

The rating for the Delirium Rating Scale Item 1 are: 1=Mild, 2=Moderate, 3=Severe

(Nakase-Richardson R S. M., Prospective evaluation of the nature, course, and impact of acute sleep abnormality following TBI , 2013) Using an Access Database, developed by [name] at the University of Washington, centers will randomize the participant into either the Bright White Light Group or the Dim Red Light Group. [46]

Light Therapy:

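### Therapy participation has inconsistent instructions on rating days and rater, no rule for which ratings are analysed, and no stated masking of the rating therapist

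*Combined protocol and SAP*

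**What the plan says.** Hypothesis 2 (Section IV) names "therapy participation (as measured by a 0-100 therapist rating" among the outcomes expected to be better with bright white light. The rating is scheduled in four places.

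- Section X.D: "evaluated at enrollment and again after light therapy (day 13", by the subject's therapist, with no discipline given.
- Section XI, Day 2: the "therapist will be asked to rate therapy participation for that day".
- Section XI, Additional Data Collected, item 2: the physical therapist is asked to "rate at both baseline days and on the final two days outcome assessment time points".
- Table 1: the row "Therapy participation" has one mark under Day 0-2 and one under Day 13.

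Section XII says that secondary outcomes "assessed at baseline and after 10 days of light therapy will be compared using repeated measures ANOVA". It gives no rule for choosing or averaging ratings.

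On masking, Section XI says that on Day 13 "a blinded Outcomes Examiner will complete the post therapy outcome assessment". The measures listed for that examiner are the Symbol Digit Modalities Test, the PANAS and the Barrow fatigue scale. Therapy participation is not among them. On the devices, it says "The cases for the BWL and RL units are visually identical".

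**The concern.** There are two separate issues.

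The first is what data are collected and used. Depending on the section followed, a patient could have one or two ratings at each end, from a physical therapist or from another therapist. Section XII then leaves the analyst to decide which ratings count as baseline and which as outcome. That decision should be fixed before results are seen. If only one rating per end is used, precision is lost although two have already been requested.

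The second is who knows the allocation. The rating is a judgement on a 0-100 scale by someone treating the patient. The one masked assessor in the plan is not listed as giving it. The light itself is white or red, so identical cases conceal nothing once the unit is on. A therapist who learned the colour could be influenced by it.

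**Working it through.** **Instructions side by side**

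| Place | Baseline | Final | Rater |
|---|---|---|---|
| X.D | Enrolment | Day 13 | Subject's therapist |
| XI, Day 2 | Day 2, for that day | not given | Therapist |
| XI, Additional Data, item 2 | Both baseline days | Final two days | Physical therapist |
| Table 1 | One mark, Day 0-2 | One mark, Day 13 | not given |

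The final time point clashes: Day 13 alone is not the final two days. The rater differs between X.D and item 2. Item 2's baseline days cannot be identified, because Section XI labels Day 0-1 as two days but puts baseline data collection on Day 2. If the final two days are Days 12 and 13, Table 1 makes Day 12 an intervention day (Days 3-12). Section XI heads light therapy Days 3-13. Those two day ranges must also be reconciled.

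**The plan's own figure.** Section VII gives an effect size of 0.5, 80% power and 128 patients (64 per group). Alpha is not stated. With an assumed two-sided 0.05, a two-sample t-test needs 63.77, so 64 per group and 128 in total. The figure reproduces. It is justified from sleep duration, not from therapy participation.

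**Gain from averaging.** The documents give no variance or correlation for this rating. Assumed:

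- r, correlation between ratings on neighbouring days at the same end: 0.5 to 0.8
- c, correlation between any baseline and any final rating: 0.3
- variance of a single rating set to 1

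The mean of two ratings has variance v = (1 + r)/2. The covariance between the baseline mean and the final mean stays at c. The residual variance in ANCOVA is therefore:

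- one rating at each end: 1 − c² = 1 − 0.09 = 0.91
- two ratings averaged at each end: v − c²/v

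| r | v | v − 0.09/v | 0.91 divided by this |
|---|---|---|---|
| 0.5 | 0.75 | 0.75 − 0.12 = 0.63 | 1.44 |
| 0.8 | 0.90 | 0.90 − 0.10 = 0.80 | 1.14 |

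Averaging is thus worth about 14% to 44% more patients for this outcome.

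**Sensitivity**

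- With c = 0.4 and the same r, the single-rating figure is 1 − 0.16 = 0.84. The averaged figures are 0.75 − 0.16/0.75 = 0.537 and 0.90 − 0.16/0.90 = 0.722. The gain is 16-57%.
- With c = 0.3 and r = 0.9, the averaged figure is 0.95 − 0.09/0.95 = 0.855, and the gain is about 6%.
- The group-by-time test in a two-time repeated measures ANOVA is a comparison of change scores. With c = 0.3 its variance is 2(1 − 0.3) = 1.4 with single ratings and 2(v − 0.3) = 0.9 to 1.2 with averages, a gain of 17-56%.
- Using v alone would give 1/0.90 = 1.11 to 1/0.75 = 1.33. That describes an unadjusted comparison of final ratings, which is neither the planned analysis nor the one recommended here.

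**The case against.** Much of the apparent conflict can be read away. Section X.D names time points and does not limit each to one rating. A Day 2 rating can be one of the baseline ratings in item 2. A single mark in Table 1 need not mean a single measurement, since actigraphy and the Makley scale also have one mark per window and run over several nights. That stands for baseline. A reader might infer that all four places contradict one another, and the text does not support that. It does not remove the clash at the final time point or over the rater.

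Sites may also be working from one rule. Table 2 lists a Manual of Procedures and research assistant training, neither of which is part of these documents. So sites could collect different data; the documents do not show that they will. If they did, a reader might infer a biased treatment comparison. Randomisation is stratified by center, so a site's schedule should fall about equally on both arms, and the cost is precision.

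On masking, a reader might infer that therapists know the arm and favour white light. The documents are silent. Sessions are set up by research or nursing staff at the bedside around breakfast, so a therapist may never see the light. Equally, nothing stated prevents it, and the quarterly staff survey in the Appendix asks rehabilitation therapists whether light therapy should be offered routinely. The exact statement is that masking is not specified.

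Finally, Aim 2 is exploratory and the trial is not sized on this outcome. That stands and limits the weight of the point.

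**Conclusion.** The point holds as a low-cost improvement to a secondary outcome. The inconsistency over the final time point and the rater, the undefined baseline days, the missing rule for which ratings are analysed and the unstated masking all rest on the text alone.

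The size rests on assumed correlations: about 14-44% more patients' worth of information for this outcome with r = 0.5-0.8 and c = 0.3, less if neighbouring days agree more closely. It should not be read as a recruitment shortfall: the primary outcome and N = 128 are unaffected. Averaging improves precision only. It does nothing about rater bias, whose size cannot be estimated from the documents and which only the masking instruction addresses.

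**What to change.** 1. Reconcile Section X.D, Table 1, the Day 2 text and item 2 of Additional Data Collected to one schedule: two named days before randomisation and two named final days. State whether Day 12 counts, since Table 1 treats it as an intervention day.
2. Name one rater per patient, of a stated discipline, for all four ratings.
3. In Section XII, specify that the mean of the final ratings is compared between arms by ANCOVA on the mean of the baseline ratings, and say what is done when one of a pair is missing.
4. Instruct research and nursing staff not to disclose the light colour to the rating therapist, and state the therapist's masking status in the protocol.

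The cost is wording and a staff instruction. Item 2 already requests two ratings at each end, so no procedure or extra rater is added. There are two downsides: patients may still reveal the colour, and a Day 12 rating, if used, would on Table 1's calendar be made while treatment is still being given.
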